16.4. ECG EVALUATIONS

Results from ECGs will be summarized by visit to the categories as recorded in the eCRF page “12-Lead-ECG” (“Normal”, “Abnormal, not clinically significant” and “Abnormal, clinically significant”).

ECG evaluations will also be listed.

16.5. VITAL SIGNS

The following Vital Signs measurements will be reported:

- Sitting Systolic Blood Pressure (mmHg)
- Sitting Diastolic Blood Pressure (mmHg)

Document: \\ieedc-vnasc01\BIOSdata\Boehringer_Ingelheim\BI_695501\NVA96252\Biostatistics\Documentation\SAP\BI1297.4 SAP FINAL v4.0_22MAY2019.docx

Author: Version Number: Final V4.0
Version Date: 22MAY2019

Template No: CS_TP_BS016 Revision 5
Effective Date: 01Apr2018

Reference: CS_WI_BS005

- Sitting Pulse Rate (bpm)
- Temperature (°C). Conversion: $\text{Temperature}(\text{°C}) = [\text{Temperature}(\text{F}) - 32] / 1.8$

Weight will be presented along with vital signs.

- Weight (kg)

The handling of retests, unscheduled, and end of trial measurements is described in Section 6.3.

The summary of actual and change from baseline by visit will be provided for vital sign data. In case of multiple measurement timepoints at one visit, the pre-injection data will be used for summary tables.

Vital signs data will be listed.

16.6. PHYSICAL EXAMINATION

Incidence of evaluation categories (Normal, Abnormal) at baseline and post-baseline visits will be provided for physical examination data.

The handling of retests, unscheduled, and end of trial measurements is described in Section 6.3.

Baseline is described in Section 6.2.

Document: \\ieedc-
vnasc01\BIOSdata\Boehringer_Ingelheim\BI_695501\NVA96252\Biostatistics\Documentation\S
AP\BI1297.4 SAP FINAL v4.0_22MAY2019.docx

Author: Version Number: Final V4.0
Version Date: 22MAY2019

Template No: CS_TP_BS016 Revision 5
Effective Date: 01Apr2018

Reference: CS_WI_BS005

Document: \\ieedc-
vnasc01\BIOSdata\Boehringer_Ingelheim\BI_695501\NVA96252\Biostatistics\Documentation\S
AP\BI1297.4 SAP FINAL v4.0_22MAY2019.docx

Author: Version Number: Final V4.0
Version Date: 22MAY2019

Template No: CS_TP_BS016 Revision 5 Reference: CS_WI_BS005
Effective Date: 01Apr2018

Document: \\ieedc-
vnasc01\BIOSdata\Boehringer_Ingelheim\BI_695501\NVA96252\Biostatistics\Documentation\S
AP\BI1297.4 SAP FINAL v4.0_22MAY2019.docx

Author: Version Number: Final V4.0
Version Date: 22MAY2019

Template No: CS_TP_BS016 Revision 5
Effective Date: 01Apr2018

Reference: CS_WI_BS005

Document: \\ieedc-
vnasc01\BIOSdata\Boehringer_Ingelheim\BI_695501\NVA96252\Biostatistics\Documentation\S
AP\BI1297.4 SAP FINAL v4.0_22MAY2019.docx

Author: Version Number: Final V4.0
Version Date: 22MAY2019

Template No: CS_TP_BS016 Revision 5
Effective Date: 01Apr2018

Reference: CS_WI_BS005

Document: \\ieedc-
vnasc01\BIOSdata\Boehringer_Ingelheim\BI_695501\NVA96252\Biostatistics\Documentation\S
AP\BI1297.4 SAP FINAL v4.0_22MAY2019.docx

Author: Version Number: Final V4.0
Version Date: 22MAY2019

Template No: CS_TP_BS016 Revision 5 Reference: CS_WI_BS005
Effective Date: 01Apr2018

Document: \\ieedc-
vnasc01\BIOSdata\Boehringer_Ingelheim\BI_695501\NVA96252\Biostatistics\Documentation\S
AP\BI1297.4 SAP FINAL v4.0_22MAY2019.docx

Author: Version Number: Final V4.0
Version Date: 22MAY2019

Template No: CS_TP_BS016 Revision 5
Effective Date: 01Apr2018

Reference: CS_WI_BS005

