Physical examination (incl. height and weight) ⁶	Х		X			X	Х
Vital signs ⁷	Х		Х	Х	Х	Х	Х
Laboratory tests (serum chemistry, hematology, urinalysis) ⁸	Х		X		Х	X	Х
Stool studies to evaluate for enteric pathogens	Х						
12-lead electrocardiogram	Х				Х	Х	Х
Previous and concomitant therapy	Х	Х	X	Х	X	X	Х
Adverse events ⁹	Х	Х	Х	Х	Х	Х	Х
EFFICACY ASSESSMENTS					•	•	
CDAI evaluation ¹⁰		Х	Х		Х	Х	
Endoscopy (mucosal ulceration, SES-CD)		Х					

TRIAL MEDICATION					
Contact IRT ¹²	Х	Х	Х	X^{13}	
Randomization		\mathbf{X}^1			
Trial medication administration ¹⁴		Х	Х	Х	

Page 9 of 93

Proprietary confidential information © 2017 Boehringer Ingelheim International GmbH or one or more of its affiliated companies

; AE: adverse event; ALT: alanine aminotransferase; AST: aspartate aminotransferase; CDAI: Crohn's disease activity index; SES-CD: Simple Endoscopic Score for Crohn's Disease; CRP: C-reactive protein; EoT: End of Treatment; HBsAg: hepatitis B surface antigen; HCV: hepatitis C virus; HIV: human immunodeficiency virus; IGRA: interferon-gamma release assay; IRT: Interactive Response Technology; SFU: safety follow-up; TB: tuberculosis; ULN: upper limit of normal.

- ¹ Patients will be randomized to each treatment in a 1:1 ratio (BI 695501: EU-approved Humira).
- ² Patients who do not achieve a clinical response at Week 4 will be excluded from the maintenance period and will have their EoT visit at Week 4. Every effort should be made for all patients who discontinue to return for a Safety Follow-up Visit 10 weeks after their last dose of trial medication.
- ³ A chest X-ray is to be taken at Screening. Alternatively, results from a chest X-ray taken within 12 weeks of Screening can be used.
- ⁴ Patients must have a negative TB screening assessment, including an IGRA (e.g., QuantiFERON[®] TB Gold). In addition, a TB test will be performed at Week 24 before switch from EU-approved Humira to BI 695501, at EoT visit, and may be performed at any time during the trial if the investigator considers it clinically necessary.
- ⁵ Females only: a serum pregnancy test at Screening and a urine pregnancy test on Day 1 (baseline); a urine pregnancy test will be performed at the applicable visits thereafter.
- ⁶ Height to be measured at Screening only; weight at every physical examination.
- ⁷ Includes measurement of blood pressure and pulse rate (both sitting after 5 minutes rest). The patient's body temperature will also be recorded.

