7.3.4 Safety analyses

Adverse events will be coded using the MedDRA coding dictionary.

Boehringer Ingelheim		12 Dec 2017
BI Trial No.: 1297.4		
c09542349-05	Trial Protocol	Page 65 of 93

All treated patients will be included in the safety analysis. In general, safety analyses will be descriptive in nature. No hypothesis testing is planned. No formal inferential analyses are planned for safety comparison. The analyses will be based on the SAF.

Statistical analysis and reporting of AEs will concentrate on treatment-emergent AEs. To this end, all AEs occurring between start of treatment and end of the REP will be considered 'treatment-emergent'. The REP is defined as 10 weeks after the last dose of trial medication. Adverse events that start before first drug intake and deteriorate under treatment will also be considered as 'treatment-emergent'. Other AEs will be assigned to the appropriate trial phases, i.e., screening or post-treatment. For patients switching from EU-approved Humira to BI 695501, AEs occurring after the first dose of BI 695501 will be assigned to BI 695501 for the overall AE analysis. AEs occurring before the first dose of BI 695501 will be assigned to the ongoing treatment.

Frequency, severity, and causal relationship of AEs will be tabulated by system organ class and preferred term after coding according to the current version of MedDRA. In addition, RR and risk difference together with 95% CIs will be presented for the overall population (details will be specified in the TSAP).

Laboratory data will be analyzed quantitatively as well as qualitatively. The latter will be done via comparison of laboratory data with their reference ranges. Values outside the reference range as well as values defined as clinically relevant will be highlighted in the listings. Treatment groups will be compared descriptively with regard to distribution parameters as well as with regard to frequency and percentage of patients with abnormal values or clinically relevant abnormal values.

Vital signs, physical examinations, or other safety-relevant data observed at screening, baseline, during the course of the trial and at the end-of-trial evaluation will be assessed with regard to possible changes compared with findings before start of treatment.

Page 66 of 93

Proprietary confidential information © 2017 Boehringer Ingelheim International GmbH or one or more of its affiliated companies

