3.3. CHANGES TO ANALYSIS FROM PROTOCOL

No change to analysis from protocol is planned.

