16.3. LABORATORY EVALUATIONS

Results from the central laboratory will be included in the reporting of this trial for Serum Chemistry, Hematology and Urinalysis. A list of laboratory assessments to be included in the outputs is included in APPENDIX 5.

Presentations will use SI and US Units.

Quantitative laboratory measurements reported as “< X”, i.e., below the lower limit of quantification (BLQ), or “> X”, i.e., above the upper limit of quantification (ULQ), will be converted to X for the purpose of quantitative summaries, but will be presented as recorded, i.e., as “< X” or “> X” in the listings.

Qualitative laboratory urinalysis results measured by central laboratory will be classified to the categories “Positive” and “Negative” based on the central laboratory normal reference.

The handling of retests, unscheduled, and end of trial measurements is described in Section 6.3. However, laboratory values taken after the first dose of trial medication up to the end of a period (i.e. up to 10 weeks after the last dose of the trial medication) will be assigned to the treatment phase for evaluation. All available data will be listed.

The following summaries will be provided for laboratory data:

- Actual and change from baseline by visit (for quantitative measurements)
- Shifts from baseline category (Low/ Normal/ High) by visit (except for urinalysis)
- Shift from baseline category (Negative/ Positive) by visit (for urinalysis)
- Listing of subjects meeting abnormal criteria
- Proportion of possible Hy’s law subjects
- Proportion of possible Drug Induced Liver Injuries (DILIs)
- The time course of alanine aminotransferase (ALT), aspartate aminotransferase (AST) and total bilirubin (TBL) for all possible Hy’s law subjects, all parameters shown on a logarithm to base 10

Document: \\ieedc-
vnasc01\BIOSdata\Boehringer_Ingelheim\BI_695501\NVA96252\Biostatistics\Documentation\S
AP\BI1297.4 SAP FINAL v4.0_22MAY2019.docx

Author: Version Number: Final V4.0
Version Date: 22MAY2019

Template No: CS_TP_BS016 Revision 5
Effective Date: 01Apr2018

Reference: CS_WI_BS005

scale of the multiple of the upper limit of normal (ULN) (Y axis) versus days since treatment start (X axis).

- Scatter plots for Evaluation of Potentially Drug-Induced Liver Injury:
 - log ALT on the X axis and log TBL on the Y axis, both shown on a logarithm to base 10 scale of the multiple of the ULN

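### ECG and physical-examination results are planned as by-visit category counts with no link to each patient's baseline, although Protocol 7.3.4 calls for assessment of change from pre-treatment findings

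*SAP*

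**What the plan says.** Protocol 7.3.4 states that vital signs, physical examinations and other safety-relevant data "will be assessed with regard to possible changes compared with findings before start of treatment". It prescribes no table format and does not name ECG in that sentence. ECG comes in as other safety-relevant data.

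The SAP treats the four domains differently:

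- Laboratory (SAP 16.3): baseline shift tables, "Shifts from baseline category (Low/ Normal/ High) by visit (except for urinalysis", with a separate negative/positive shift for urinalysis.
- Vital signs (SAP 16.5): "The summary of actual and change from baseline by visit will be provided for vital sign data".
- ECG (SAP 16.4): "Results from ECGs will be summarized by visit to the categories as recorded in the eCRF page", in three categories, and "ECG evaluations will also be listed".
- Physical examination (SAP 16.6): "Incidence of evaluation categories (Normal, Abnormal) at baseline and post-baseline visits will be provided for physical examination data". No shift table and no listing are named.

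SAP 3.3 declares: "No change to analysis from protocol is planned".

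On who remains in the trial, Flow Chart A footnote 2 says: "Patients who do not achieve a clinical response at Week 4 will be excluded from the maintenance period and will have their EoT visit". For these patients that visit falls in Week 4. SAP 6.3 places early-termination data in the End of Treatment (EoT) row of by-visit tables.

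**The concern.** A count of normal and abnormal patients at each visit is a set of margins. It does not say whether the patients abnormal at Week 24 are those who were abnormal before treatment. Equal counts at two visits can mean that nobody changed, or that several patients became abnormal while as many resolved.

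The rows also describe different patients. The baseline row holds everyone treated. For patients who continue, the first on-treatment physical examination is at Week 24, after the Week 4 non-responders have gone. The EoT row brings those non-responders back and mixes them with patients treated for 48 weeks. In the Humira arm, that puts patients who never received BI 695501 in the same row as patients who switched to it. Apart from safety follow-up, EoT is the only scheduled ECG and physical-examination row after the switch, and Protocol 2.1 names switching as something the trial will address.

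**Working it through.** The plan states no figure to reproduce here. The check sets the schedule beside the tables and adds illustrative arithmetic. The documents give no abnormality rates, so **all such rates below are assumptions**.

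**Inputs from the documents.** 65 patients per arm and 80% Week 4 response in both arms (Protocol 7.7). A pooled historical adalimumab response of 54.1% (Protocol Appendix 10.3), used as a lower alternative.

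**1. Which rows lose the non-responders.** From the flow charts and Protocol 6.2.2:

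| Row | Physical examination | ECG |
|---|---|---|
| Week 4 | not scheduled as a visit row | before exit, all still treated |
| Week 8 | not scheduled | Week 4 responders only |
| Week 24 (before that day's dose) | Week 4 responders only | Week 4 responders only |
| EoT | Week 4 exits and later leavers or completers pooled | same |
| Safety follow-up | all asked to return | all asked to return |

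The loss therefore acts on physical examination at Week 24 and on ECG at Weeks 8 and 24. It acts on safety follow-up only through non-attendance.

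**2. How many leave.** At 80% response, 0.80 × 65 = 52 continue and 13 leave per arm (26 of 130). At 54.1%, 0.541 × 130 ≈ 70 continue and about 60 leave.

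**3. What the counts leave open.** Among N patients seen at both visits, with A0 abnormal at baseline and A24 abnormal at Week 24, the number newly abnormal lies between max(0, A24 − A0) and min(A24, N − A0). Take N = 52 and, as an assumption, A0 = A24 = 13. The lower bound is max(0, 0) = 0 and the upper bound is min(13, 39) = 13. The counts fit anything from 0 to 13 new abnormalities among the 39 who were normal. The planned table is less informative still, because its baseline row covers all treated patients and does not give A0 for those who continue.

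**4. When attrition moves the percentage.** Let r be the response rate, pR the abnormal rate in responders and pN that in non-responders. With no change in any patient, the baseline row shows r·pR + (1 − r)·pN and the Week 24 row shows pR.

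| Assumed pR, pN | 80% response | 54.1% response |
|---|---|---|
| 20%, 20% | 20.0% → 20.0% | 20.0% → 20.0% |
| 20%, 30% | 22.0% → 20.0% | 24.6% → 20.0% |
| 20%, 40% | 24.0% → 20.0% | 29.2% → 20.0% |
| 30%, 20% | 28.0% → 30.0% | 25.4% → 30.0% |

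For example, 0.80 × 0.20 + 0.20 × 0.40 = 24.0%. Equal rates give no shift. Unequal rates give a shift in either direction.

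**5. Composition of the EoT row.** Suppose every Humira patient attends an EoT visit. Week 4 exits are then 13/65 = 20% of that row at 80% response. At 54.1% they are 0.459 × 65 ≈ 30 of 65, or about 46%. None of them has received BI 695501.

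**The case against.** The strongest reply is that change is captured elsewhere, and most of this stands. Protocol 5.3.1, 5.3.4 and 5.3.6.2 have clinically relevant physical-examination and ECG findings reported as adverse events, with pre-existing ones recorded as baseline conditions. They then enter the treatment-emergent tables, which SAP 16.1.2 splits at Week 24. ECGs are listed by patient. Exclusion criterion 24a removes clinically significant ECG abnormalities at Screening, so apart from eligibility violations a later count in that category is new. A reader might infer that new abnormalities go unseen, and the documents do not support that. What remains is narrower: physical-examination findings, and ECG changes, that the investigator does not judge clinically relevant. A listing also does not summarise change by arm.

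A reader might also infer that losing non-responders distorts the percentages by itself. It does so only if abnormality rates differ between responders and non-responders, and only in the rows identified above. If the arms share the same response rate and the same rates within response groups, both move alike.

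Nor is an outright breach of the protocol shown. Section 7.3.4 asks for an assessment of possible change without fixing a format, and tabulating baseline beside later visits is a minimal way to do it. Finally, SAP 8 refers to table templates that are not in the documents at hand. A shift layout or an examination listing there cannot be excluded. SAP 16.3 does, however, state its shift tables in the body of the plan, whereas 16.4 and 16.6 state none.

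**Conclusion.** The point holds in a limited form. As written, SAP 16.4 and 16.6 specify no baseline-linked summary for ECG or physical examination, although the protocol asks for assessment of change and the SAP provides such a summary for laboratory data and vital signs. That by-visit counts cannot identify who changed does not depend on any assumed rate. The size of any shift from attrition does: in the examples it ranges from 0 to 9.2 points, with the direction set by which group has more abnormalities. The pooling at EoT follows from SAP 6.3 and the flow charts. Its 20% and 46% figures assume full EoT attendance and the two response rates used.

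Severity is minor. This is descriptive safety output in an exploratory trial, clinically relevant findings are reported as adverse events, and the primary analysis is untouched.

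**What to change.** In SAP 16.4 and 16.6:

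- Add shift tables by randomized arm from the last pre-dose category (the SAP 6.2 baseline) to each post-baseline visit, among patients with both values. Use three categories for ECG and two for physical examination.
- Add shifts to the worst post-baseline category, separately before and after the Week 24 switch. Count Week 24 assessments as pre-switch, since they precede that day's dose, and keep patients who left before Week 24 in the pre-switch part.
- In the EoT row, show Week 4 exits separately from later EoT visits.
- Add a physical-examination listing to 16.6.

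If the templates already contain these displays, a sentence in each section naming them is enough. Otherwise the cost is SAP wording and a small set of tables in the format already planned for laboratory data, with no new data collection.

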APPENDIX 1. PROGRAMMING CONVENTIONS FOR OUTPUTS

OUTPUT CONVENTIONS

Output File Naming Conventions

File names should only consist of lowercase letters, digits (0 to 9) and hyphens. A period should only be used to indicate a separator between the file name and the extension. No spaces, other special characters or punctuation marks are permitted.

The program, program log and output file name should reflect the type of the statistical output. The output files will contain the output number in addition. If this is not possible, then the output name should be at least as descriptive as possible. A prefix can be used to distinguish between a Table, Listing and Figure document ('t' for table, 'l' for listing and 'f' for figure). If there is only 1 digit in the number of the table, listing or figure in the place where 2 digits are possible, a leading zero should be added in the file name to make sorting consistent with the sequence (eg t-14-3-01-1.RTF)

As far as possible, output files should be in RTF format.

The outputs will be provided in pdf format.

PAPER SIZE, ORIENTATION AND MARGINS

The size of paper will be Letter.

The page orientation should preferably be landscape, but portrait is also permitted.

Margins should provide at least 1 inch (2.54 centimeters) of white space all around the page, regardless of the paper size.

The number of columns per page (linesize) should 134 for Letter.

The number of rows per page (pagesize) should be 40 for Letter.

FONTS

The font type 'Courier New' should be used as a default for tables and listings, with a font size of 8. The font color should be black. No bolding, underlining, italics or subscripting should be permitted. Try to avoid using

Document:	\\ieedc-vnasc01\BIOSdata\Boehringer_Ingelheim\BI_695501\NVA96252\Biostatistics\Documentation\SAP\BI1297.4 SAP FINAL v4.0_22MAY2019.docx		
Author:	Version Number:	Final V4.0	
	Version Date:	22MAY2019	
Template No:	CS_TP_BS016	Revision 5	Reference: CS_WI_BS005
Effective Date:	01Apr2018		

Copyright © 2009, 2010, 2012, 2016, 2018 All rights reserved. The contents of this document are confidential and proprietary to Holdings Inc. and its subsidiaries. Unauthorized use, disclosure or reproduction is strictly prohibited.

superscripts, unless absolutely necessary. Single spacing should be used for all text.

Figures should have a default font of “Times New Roman”, “Helvetica”, or “Courier New”.

This can be achieved by using the following options in SAS:

```
goptions
gunit = pct
cback = white
colors = (black)
hby = 2.4
ftext = "TimesRoman"
htext = 2.5;
```

HEADER INFORMATION

Headers should be defined as follows:

- The header should be placed at the top of the page (same place on each page) regardless of the size or orientation of the table or listing
- The customer name and protocol number should appear in row 1, left-aligned
- The output identification number should appear in row 2, left-aligned
- The output title should start in row 2 after output identification number separated by a double dot, left-aligned
- The output population should appear in row 2 after output title separated by a dash, left-aligned. The population should not be spelled out in full, e.g. FAS in preference to Full analysis set.
- Row 3 should be a continuous row of underscores ('_') (the number of underscores should equal the linesize)
- Row 4 should be a blank line
- Mixed case should be used for titles
- The output titles should be designed so that they are arranged consistently through all outputs. For example, content (e.g., Vital Signs) followed by metric (e.g., Change from Baseline) e.g. Vital Signs – Change from Baseline.
- Titles should not contain quotation marks or footnote references
- The column headings should be underlined with a row of underscores ('_')
- Column headings spanning more than one column should be underlined and have underscores on either side of the title and should be centered
- Column headings containing numbers should be centered
- Column headings should be in sentence case
- In general, the population count should appear in the column header in the form “(N=XXX)”
- “Statistic” should be the column header over n, Mean, SE, n (%) etc.
- As a rule, all columns should have column headings.

Document:	\\ieedc-vnasc01\BIOSdata\Boehringer_Ingelheim\BI_695501\NVA96252\Biostatistics\Documentation\SAP\BI1297.4 SAP FINAL v4.0_22MAY2019.docx		
Author:	Version Number:	Final V4.0	
	Version Date:	22MAY2019	
Template No:	CS_TP_BS016	Revision 5	Reference: CS_WI_BS005
Effective Date:	01Apr2018		

TABLE AND LISTING OUTPUT CONVENTIONS

General:

- The first row in the body of the table or listing should be blank
- The left hand column should start in column 1. No indenting or centering of the output should occur.
- Rounding should be done with the SAS function ROUND, if no further specification.
- Numbers in tables should be rounded, not truncated, if no further specification.
- Alphanumeric output should be left aligned.
- Numbers should be decimal point aligned.
- Whole numbers should be right aligned.
- Text values should be left aligned.
- The first letter of a text entry should be capitalized
- Listings of adverse events, concomitant medications, medical histories etc. should be sorted in chronological order, with earliest adverse event, medication or history coming first.
- The trial drug should appear first in tables with treatments as columns
- In general, only present totals (across treatment groups) at baseline/randomization, and do not present them post randomization.
- If possible, include 100% frequencies in the table shell, so that it is clear what the denominator is for percentage calculations.
- All listing outputs should be sorted (preferably by Treatment, Site Number and Subject Number).
- Do not use superscripts and subscripts
- The width of the entire output should match the linesize option

Univariate Statistics:

- Statistics should be presented in the same order across tables (i.e., n, Mean, SD, Median, IQR, Minimum, Maximum or n, gMean, gCV, Mean, CV, SD, Median, Minimum, Maximum)
- Table statistics should line up under the N part of the (N=XXX) in the table header. All decimal points should line up. If the minimum and maximum are output on one line as Minimum, Maximum then the comma should line up with the decimal point.
- If the original data has N decimal places, then the summary statistics should have the following decimal places:
 - Minimum and maximum: N
 - Mean, gMean, median, gCV% and CV%: N + 1
 - SD, IQR: N + 2

Frequencies and percentages (n and %):

- Percent values should be reported inside parentheses, with one space between the count and the left parenthesis of the percentage. Parentheses should be justified to accept a maximum of 100.0 as a value and padded with blank space if the percent is less than 100.0. An example is given below:
77 (100.0%)

Document: \\ieedc-
vnasc01\BIOSdata\Boehringer_Ingelheim\BI_695501\NVA96252\Biostatistics\Documentation\S
AP\BI1297.4 SAP FINAL v4.0_22MAY2019.docx

Author: Version Number: Final V4.0
Version Date: 22MAY2019

Template No: CS_TP_BS016 Revision 5
Effective Date: 01Apr2018

Reference: CS_WI_BS005

Statistical Analysis Plan

50 (64.9%)

0 (0.0%)

- Percentages will be reported to one decimal place, except percents <100.0% but >99.9% will be presented as '>99.9%' (e.g., 99.99% is presented as >99.9%); and percents < 0.1% will be presented as '<0.1%' (e.g., 0.08% is presented as <0.1%). Rounding will be applied after the <0.1% and >99.9% rule.

E.g., (<0.1%)

(6.8%)

(>99.9%)

- Percentages may be reported to 0 decimal places as appropriate (for example, where the denominator is relatively small).
- Where counts are zero, percentages of 0.0% should appear in the output.

Confidence Intervals:

- As a rule confidence intervals are output to one place more than the raw data, and standard deviations and standard errors to two places more than the raw data
- Confidence intervals should be justified so that parentheses displayed on consecutive lines of a table "line up".
- Boundary values of confidence intervals should be separated by a comma.
- Boundary values should be padded as necessary to accept negative values and to allow alignment of the decimal place.
- An example is given below:
(-0.12, -0.10)
(9.54, 12.91)

P-values:

- P-values should be reported to three decimal places, except values <1.000 but >0.999 will be presented as '>0.999' (e.g., 0.9998 is presented as >0.999); and values <0.001 will be presented as '<0.001' (e.g., 0.0009 is presented as <0.001). Rounding will be applied after the <0.001 and >0.999 rule

Ratios:

- Ratios should be reported to one more decimal place than the original data.

Spacing:

- There must be a minimum of 1 blank space between columns (preferably 2)

Denominators:

- If a different count other than the population count is used for a denominator (within the table) to calculate percentages, there should be a row in the table that identifies that number "n".
- Alternatively, a footnote should be included in each table with percentages to indicate the denominator for percentages.

Missing values

- A "0" should be used to indicate a zero frequency.

Document: \\ieedc-
vnasc01\BIOSdata\Boehringer_Ingelheim\BI_695501\NVA96252\Biostatistics\Documentation\S
AP\BI1297.4 SAP FINAL v4.0_22MAY2019.docx

Author: Version Number: Final V4.0
Version Date: 22MAY2019

Template No: CS_TP_BS016 Revision 5
Effective Date: 01Apr2018

Reference: CS_WI_BS005

- A blank will be used to indicate missing data in an end-of-text table or subject listing.

FIGURE OUTPUT CONVENTIONS

- Figures will be provided in PDF files using the SAS Output Delivery System (ODS) as generated by SAS.
- The image should be clear and of high quality when viewed in the Word document, and when printed.
- In general, boxes around the figures should be used.

FOOTNOTE INFORMATION

Footers should be defined as follows:

- A continuous line of underscores (‘_’) will follow the body of the table or listing prior to any footnotes at the bottom of the page
- Table footnotes should be defined using compute statements in the proc report, and should appear directly after the body of the table
- The program path and name and version number (if applicable) should appear as footnote 1 at the bottom of the page
- The date/time stamp should appear as footnote 2 at the bottom of the page
- Footnotes should be left-aligned.
- Footnotes should be in sentence case.
- Only “typewriter” symbols are permitted – e.g., “*”, “\$”, “#”, “@”, “&” and “+”.
- The choice of footnote symbols should be consistent. E.g., if you have the footnote “# indicates last observation carried forward” for one table, the same symbol and footnote should indicate LOCF for all tables.
- If text wraps across more than one line (for a note), the first letter for all lines of text after the first one will be indented to align beneath the first letter of the text in the first line.
- The page identification in the format Page X of Y (where Y is the total number of pages for the output) should appear in the footer, right aligned.

Ordering of footnotes should be as follows:

- 1.) Source data listing reference, if necessary
 - 2.) Abbreviations and definitions
 - 3.) Formulae
 - 4.) P-value significance footnote
 - 5.) Symbols
 - 6.) Specific notes
- Common notes from table to table should appear in the same order.

The symbols should appear in the same order as they are defined in the table or listing, from left to right.

Document:	\\ieedc-vnasc01\BIOSdata\Boehringer_Ingelheim\BI_695501\NVA96252\Biostatistics\Documentation\SAP\BI1297.4 SAP FINAL v4.0_22MAY2019.docx		
Author:	Version Number:	Final V4.0	
	Version Date:	22MAY2019	
Template No:	CS_TP_BS016	Revision	5
Effective Date:	01Apr2018		Reference: CS_WI_BS005

DATES & TIMES

Depending on data available, dates and times will take the form yyyy-mm-ddThh:mm:ss.

SPELLING FORMAT

English US.

PRESENTATION OF TREATMENT GROUPS

For outputs, treatment groups will be represented as follows and in that order:

Treatment Group	For Tables and Graphs
BI 695501	BI 695501
EU-approved Humira	Humira

PRESENTATION OF VISITS

For outputs, visits will be represented as follows and in that order:

Long Name (default)	Short Name	Visits as per protocol
Day -28 to -14	D-28 to -14	
Day 1	D1	Baseline
Day 15	D15	Day 15 (Week 2)
...
Day 337	D337

LISTINGS

All listings will be ordered by the following (unless otherwise indicated in the template):

- randomized treatment group (or treatment received if it's a safety output)

Document: \\ieedc-vnasc01\BIOSdata\Boehringer_Ingelheim\BI_695501\NVA96252\Biostatistics\Documentation\SAP\BI1297.4 SAP FINAL v4.0_22MAY2019.docx

Author: Version Number: Final V4.0
Version Date: 22MAY2019

Template No: CS_TP_BS016 Revision 5
Effective Date: 01Apr2018

Reference: CS_WI_BS005

- center-subject ID
- date including Study Day (where applicable),
- For listings where non-randomized subjects are included, these will appear in a category after the randomized treatment groups labeled 'Not Randomized'.

The visit as recorded in the eCRF will be displayed in the listings (and not the remapped visit).

